11.4. Unscheduled Assessments and Assignment of Data to Visit Windows

Unscheduled Assessments

The determination of values for by-visit analyses for both efficacy and safety variables will be based on assessments available from scheduled visits, or from unscheduled visits if the scheduled visit was not performed.

Extra assessments (e.g., laboratory data or vital signs associated with non-protocol-specified visits or obtained in the course of investigating or managing AEs) will be included in data listings, but not in summaries except for the endpoint determination. If more than one laboratory value is available for a given visit, the first observation will be used in summaries.

Assignment of Data to Visit Windows

Data analyzed by visit (including efficacy, laboratory, vital signs, ECG, ADA, etc.) will be summarized by the study scheduled visits described in the Schedule of Time and Events in Appendix 14.2.

The analysis visit windows are created per the Schedule of Time and Events for each parameter and will only be applied if the data from the study scheduled visits are unavailable. The following general, hierarchical rules will be applied for mapping the unscheduled visits and/or the early termination visit, EOT visit, or EOS visit (which will subsequently be collectively referred to as the “early termination of treatment or study” [ETTS] visit) for each parameter.

Note that the EOT visit is coded as “Week 52/ Visit 28” for all patients, regardless of the variable 24-52-week treatment period.

1. If the ETTS visit falls in an analysis window which already has an observed value of the parameter from the scheduled visit, the ETTS visit will be mapped to the next scheduled visit, provided there is no observed value of the parameter at the next scheduled visit.
2. If there is no observed value of the parameter from the scheduled visit and if both the ETTS visit and 1 or more unscheduled visits of the parameter are available in the same analysis visit window, only the ETTS visit may be mapped to a scheduled visit.
 - a. Note: If at least 2 of the EOT, EOS, and early termination visits are available in the same analysis visit window, then the ETTS visit to be mapped to the scheduled visit will be selected in the following hierarchical order: EOT visit, EOS visit, early termination visit.
3. If there is no observed value of the parameter from the scheduled visit and if there is no ETTS visit but 1 or more unscheduled visits of the parameter available in an analysis visit window, then the following rules will be applied to map the unscheduled visit to the scheduled visit:
 - b. If there is only 1 unscheduled visit of the parameter in the analysis visit window, it will be mapped to the scheduled visit.
 - c. If there are 2 or more unscheduled visits of the parameter in the analysis visit window, the closest unscheduled visit to the target day will be mapped to the scheduled visit. If 2 or more unscheduled visits are equidistant from the target day, with 1 unscheduled visit occurring prior to and 1 unscheduled visit occurring after the target day, the unscheduled visit occurring after the target day will be selected for mapping to the scheduled visit. If there are 2 or more unscheduled visits that occur on the same day closest to the target day, the average of the parameter values will be mapped to the scheduled visit and used for analysis.

The ETTS and unscheduled visits will be mapped to scheduled visits per the analysis visit windows defined in [Table 3](#) based on the study relative day of each parameter. Only ETTS and unscheduled visits that occur within the analysis visit windows defined in [Table 3](#) will be eligible to be mapped to a scheduled visit.

Table 3: Analysis Visit Windows by Parameter for ETTS/Unscheduled Visit Mapping

Week (Sched- uled Visit)	Target Day	Visit Window for Analysis Parameters					
		Spirometry, FeNO	ACQ-5	SGRQ, Serum A fumigatus -specific IgE, [REDACTED] [REDACTED] Physical Examination	Vital Signs	Serum Total IgE, Hematology, Blood Chemistry, Urinalysis, ECG, [REDACTED]	Drug Concentration Sample, ADA Sample
0	1	≤1	≤1	≤1	≤1	≤1	≤1
2	15	[2, 22]	[2, 22]		[2, 22]		
4	29	[23, 36]	[23, 36]	[2, 56]	[23, 36]	[2, 43]	
6	43	[37, 50]	[37, 50]		[37, 50]		
8	57	[51, 64]	[51, 64]		[51, 64]	[44, 71]	
10	71	[65, 78]	[65, 78]		[65, 78]		
12	85	[79, 92]	[79, 92]	[57, 113]	[79, 92]	[72, 113]	[2, 126]
14	99	[93, 106]	[93, 106]		[93, 106]		
16	113	[107, 120]	[107, 127]		[107, 140]		
24	169	[121, 197]	[155, 183]	[141, 197]	[141, 197]	[141, 197]	[127, 210]
36	253	[198, 295]	[239, 267]	[225, 280]	[225, 280]	[225, 280]	
44	309	[296, 337]	[295, 323]		[281, 337]	[281, 337]	
52	365	[338, 393]	[351, 379]	[338, 393]	[338, 393]	[338, 393]	[211, 462]

Note: For a given parameter, only the analysis windows corresponding to the visits that will be summarized/analyzed for that given parameter (per Section 7) are applicable.

ACQ-5=Asthma Control Questionnaire 5-item version; ADA=anti-drug antibody; *A fumigatus*=*aspergillus fumigatus*; [REDACTED]; ECG=electrocardiography; ETTS=early termination of treatment or study; FeNO=fractional exhaled nitric oxide; [REDACTED]; IgE=immunoglobulin E; SGRQ=St. George's Respiratory Questionnaire; [REDACTED].

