### 3.2. Rationale

#### 3.2.1. Rationale for Study Design

This study is designed to investigate the efficacy and safety of dupilumab in patients with ABPA.

A double-blinded, randomized trial design is chosen to minimize bias in data collection and result interpretation. The presence of a placebo arm is appropriate for the objectives of this study as this will allow for the most robust assessment of the efficacy and safety of dupilumab. Although dupilumab has been shown to be efficacious and safe to treat patients with moderate-to-severe asthma, neither the safety nor the efficacy of dupilumab for ABPA in patients who have asthma has been established. In contrast to asthma, ABPA is characterized by irreversible airway damage and parenchymal involvement, thus the known efficacy of dupilumab on key asthma outcomes cannot be easily extrapolated to ABPA. In addition, all patients will be allowed to receive rescue treatment with systemic corticosteroids (standard of care) and antifungal therapy (widely though not universally used) as necessary and will be closely monitored throughout the study. The proposed treatment duration of at least 24 and no more than 52 weeks provides an opportunity to assess the impact of dupilumab on multiple clinical outcome measures of ABPA including long-term changes in lung function; symptom control; rate of severe respiratory exacerbations; and pharmacodynamic (PD) effects on biomarkers of type 2 inflammation

in ABPA, including serum total and *A fumigatus*-specific IgE levels. Patients will be treated for a minimum of 24 weeks and a maximum of 52 weeks. Details on the variable treatment period can be found in Section 9.1.1.

A 12-week post-treatment safety follow-up period is chosen based on the time expected for dupilumab drug levels to reach below the lower limit of quantification after the last dose of the drug.

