#### **Post-Treatment Follow-Up Period:**

Upon completing the randomized treatment period, patients will continue their background therapy and enter a 12-week safety follow-up period. Adjustment of background asthma and ABPA medications will be allowed at the discretion of the investigator as clinically indicated during the post-treatment follow-up period.

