#### 9.1.1. Footnotes for the Schedule of Events Table

#### Footnotes for Table 1 Schedule of Events

\*Visits 5, 7, 9, and 10 will be performed as phone visits for patients not receiving OCS at baseline. For patients receiving OCS at baseline, these visits should be performed in-clinic if the patient remains on OCS on the day of the clinic visit. If OCS has been discontinued, these visits can be either in-clinic or performed as a phone visit at the discretion of the investigator. Assessments/procedures marked with an asterisk should only be performed if the visit occurs in-clinic.

\*\*After the last patient has completed visit 14/week 24 of the treatment period or withdrawn from the study, all patients still currently in the treatment period (between visit 15/week 26 and visit 27/week 50) should return to the clinic 2 weeks from their last dose/treatment administration to complete their EOT visit and all its applicable assessments. For patients who have withdrawn from the study treatment but remain in the study, the EOT visit will take place 2 weeks from their last visit. All patients must have their EOS visit 12 weeks after their EOT visit.

- a. Prior to screening, patients must be on a stable background therapy for asthma which may include ICS in combination with a second controller medication (eg, LABA, LTRA, theophylline, etc) for at least 3 months with a stable dose ≥1 month prior to baseline. Patients requiring a third controller are allowed to participate in this study. The third controller should also be used for at least 3 months with a stable dose ≥1 month prior to visit 1. Patients requiring systemic steroids of up to 10 mg per day (or up to 30 mg every alternate day) as controller medication are permitted.
- b. Randomization/baseline visit is defined as day 1. The visit schedule should be adhered to within  $\pm 1$  week for the screening period,  $\pm 3$  days for the randomized IMP treatment period, and  $\pm 7$  days for the post-IMP treatment period.
- c. All assessments at visit 2 (day 1) are to be conducted pre-IMP dose except for the assessment of local tolerability of SC injections.

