7.1.4. SGRQ Total Score

The SGRQ PRO instrument is administered at baseline, Weeks 4, 12, 24, 36, and at EOT and EOS. Derivation of the total score for each patient at each time point of administration is described in Appendix 14.5. A secondary PRO endpoint is the absolute change from baseline in the SGRQ total score over the 24-52-week treatment period.

The proportion of participants achieving a reduction in the SGRQ total score of ≥ 4 points from baseline at Weeks 12, 24, 36, and 52 will also be assessed as a secondary PRO endpoint.

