Visit	1	2 ^c	3	4	5*	6	7*	8	9*	10*	11	12	13	14	15	16	17	18	19	20	21	22	23	24	25	26	27	14-28	15-29
Window (days) (optional)	±7	±3	±3	±3	±3	±3	±3	±3	±3	±3	±3	±3	±3	±3	±3	±3	±3	±3	±3	±3	±3	±3	±3	±3	±3	±3	±3	±7	
Blood immunophenotyping substudy ^y (optional)		X		X				X																				X	

NOTE: EOS is end of study; the follow-up period begins at the EOT visit and ends at the EOS visit.

Footnotes for the Schedule of Time and Events

*Visits 5, 7, 9, and 10 will be performed as phone visits for patients not receiving OCS at baseline. For patients receiving OCS at baseline, these visits should be performed in-clinic if the patient remains on OCS on the day of the clinic visit. If OCS has been discontinued, these visits can be either in-clinic or performed as a phone visit at the discretion of the investigator. Assessments/procedures marked with an asterisk should only be performed if the visit occurs in-clinic.

**After the last patient has completed visit 14/week 24 of the treatment period or withdrawn from the study, all patients still currently in the treatment period (between visit 15/week 25 and visit 27/week 50) should return to the clinic 2 weeks from their last dose/treatment administration to complete their EOT visit and all its applicable assessments. For patients who have withdrawn from the study treatment but remain in the study, the EOT visit will take place 2 weeks from their last visit. All patients must have their EOS visit 12 weeks after their EOT visit.

- Prior to screening, patients must be on a stable background therapy for asthma which may include ICS in combination with a second controller medication (eg, LABA, LTRA, theophylline, etc) for at least 3 months with a stable dose \geq 1 month prior to baseline. Patients requiring a third controller are allowed to participate in this study. The third controller should also be used for at least 3 months with a stable dose \geq 1 month prior to visit 1. Patients requiring systemic steroids of up to 10 mg per day (or up to 30 mg every alternate day) as controller medication are permitted.

- b. Randomization/baseline visit is defined as day 1. The visit schedule should be adhered to within ± 1 week for the screening period, ± 3 days for the randomized IMP treatment period, and ± 7 days for the post-IMP treatment period.
- c. All assessments at visit 2 (day 1) are to be conducted pre-IMP dose except for the assessment of local tolerability of SC injections.

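### SAP 11.4 lets the end-of-study visit, 14 weeks after the last dose, fill empty Week 36, 44 and 52 cells when treatment was shortened

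*SAP*

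**What the plan says.** SAP 11.4 groups the early termination, EOT and EOS visits as ETTS visits: "The following general, hierarchical rules will be applied for mapping the unscheduled visits and/or the early termination visit, EOT visit, or EOS visit". The windows in SAP Table 3 apply only when the scheduled value is missing. To be mapped, an ETTS visit needs only a study day inside one of them.

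Two rules matter here. Rule 1 covers a window that already holds a scheduled value: "the ETTS visit will be mapped to the next scheduled visit, provided there is no observed value of the parameter at the next scheduled visit". Rule 2a ranks EOT over EOS over early termination, but only when they fall in the same window. A note adds that EOT is coded as Week 52, Visit 28 "for all patients, regardless of the variable 24-52-week treatment period".

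On timing, the EOT visit for patients stopped by the cut-off is 2 weeks after the last dose (Protocol 9.1.1 and 9.1.4), and "All patients must have their EOS visit 12 weeks after their EOT visit". The schedule note in SAP 14.2 states that "the follow-up period begins at the EOT visit and ends at the EOS visit". Protocol 3.2.1 explains the length of follow-up: "A 12-week post-treatment safety follow-up period is chosen based on the time expected for dupilumab drug levels to reach below the lower limit of quantification". Protocol 6.1 adds: "Adjustment of background asthma and ABPA medications will be allowed at the discretion of the investigator as clinically indicated during the post-treatment follow-up period".

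SAP 14.1 defines the ACQ-5, SGRQ, IgE and FeNO summaries at time points within the treatment period. The SGRQ responder proportion is required at Weeks 12, 24, 36 and 52, while SAP 7.1.4 says "The SGRQ PRO instrument is administered at baseline, Weeks 4, 12, 24, 36, and at EOT and EOS".

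**The concern.** By the protocol's own design, EOS is a washout measurement, taken after a period in which background therapy may have changed. Treatment ends at 52 weeks or when the last patient reaches Week 24, so shortened treatment is built in. Shortened patients have exactly the empty late cells that section 11.4 fills. The late columns for secondary endpoints 4 to 9 can then hold on-treatment values, EOT values carried to a later label, and off-drug EOS values, all under one week heading. Durability of effect, and the SGRQ responder rates at Weeks 36 and 52, could not be read as on-treatment results.

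A second problem is the status of the Week 52 coding. If it is only a database label, EOT is placed by study day. If it counts as an observed Week 52 value, every shortened EOT is reported as Week 52. The SAP does not say which applies. SGRQ has no Week 52 collection apart from EOT, so its Week 52 responder cell depends entirely on the answer.

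**Working it through.** **Inputs.** EOT is 2 weeks after the last dose and EOS is 12 weeks after EOT (Protocol 9.1.1). EOT falls in Weeks 24 to 52. Windows are from SAP Table 3:

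| Cell | FeNO | ACQ-5 | SGRQ, A fumigatus IgE, total IgE |
|---|---|---|---|
| Week 24 | 121–197 | 155–183 | 141–197 |
| Week 36 | 198–295 | 239–267 | 225–280 |
| Week 44 | 296–337 | 295–323 | not applicable |
| Week 52 | 338–393 | 351–379 | 338–393 |

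SGRQ and A fumigatus IgE have no Week 44 window. Total IgE has one, but it is not collected at Week 44, and the note under Table 3 makes that window inapplicable.

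**Reproducing the plan's figures.** Study day = 7 × week + 1 gives 169, 253, 309 and 365 for Weeks 24, 36, 44 and 52, the Table 3 target days. EOS week = EOT week + 12 gives 36 to 64, the protocol's stated study duration. EOS is 2 + 12 = 14 weeks after the last dose.

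**Assumptions.** Nominal days; EOS day = EOT day + 84; scheduled visits before the EOT week observed; an EOT at Week 24, 36 or 44 taken as that scheduled visit.

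**Two examples, EOT placed by study day.**
- EOT at Week 24: EOS day = 169 + 84 = 253, the Week 36 target. EOS becomes Week 36 for all five measures.
- EOT at Week 40: EOT day = 281, one day past the SGRQ Week 36 window, so the on-treatment SGRQ is unused. EOS day = 281 + 84 = 365, so the off-drug SGRQ becomes Week 52.

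**All 14 shortened EOT weeks (24, 26, …, 50), EOS filling a cell uncontested:**

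| | EOT placed by study day | Week 52 code counts as observed |
|---|---|---|
| FeNO | 8: EOT 24 → Wk 36; 32, 34, 36 → Wk 44; 38, 40, 42, 44 → Wk 52 | 7: EOT 24–30 → Wk 36; 32–36 → Wk 44 |
| ACQ-5 | 7: EOT 24 → Wk 36; 30, 32, 34 → Wk 44; 38, 40, 42 → Wk 52 | 5: EOT 24, 26 → Wk 36; 30, 32, 34 → Wk 44 |
| SGRQ, both IgE | 4: EOT 24 → Wk 36; 40, 42, 44 → Wk 52 | 2: EOT 24, 26 → Wk 36 |

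From EOT Week 46 the nominal EOS day is at least 323 + 84 = 407, beyond every window above.

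**Unresolved collisions (study-day reading).** Rule 1 moves EOT into a cell that EOS reaches directly, and rule 2a does not apply because the two started in different windows. This happens at EOT Weeks 26 and 28 (FeNO), 26 (ACQ-5), and 26 and 38 (SGRQ, IgE).

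**Mistimed EOT values.** Under the study-day reading, rule 1 can move an on-treatment SGRQ from Week 38 (day 267, Week 36 already filled) to Week 52, which is 14 weeks. Under the coding reading, every shortened EOT is labelled Week 52, wrong by 52 − 50 = 2 to 52 − 24 = 28 weeks.

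**Sensitivity.**
- Dropping EOT Week 24, since the protocol footnote covers Weeks 26 to 50, gives 7, 6 and 3 of 13 (study day) or 6, 4 and 1 (coding).
- If the Week 24, 36 or 44 scheduled visit is observed separately from EOT, the study-day counts fall to 5, 6 and 3, the rest becoming collisions.
- With EOT ±3 and EOS ±7 days (7 × 15 = 105 combinations per EOT week), the number of EOT weeks affected at every combination versus at any combination is: FeNO 7 to 9 (study day) or 6 to 7 (coding); ACQ-5 3 to 8 or 2 to 5; SGRQ and IgE 2 to 6 or 2 to 3.

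**Drug concentration.** The Week 52 window is days 211–462. EOS fills it uncontested only at EOT Week 24, with collisions at Weeks 26 and 28; under the coding reading it never does.

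**The case against.** The strongest reply accepts that EOS is mappable and argues that the effect is narrow.

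- The study-day reading is the more natural one. Rule 2a ranks EOT first, which would serve little purpose if EOT already counted as an observed Week 52 value. On that reading EOS fills Week 36 uncontested only at EOT Week 24, which needs a patient randomised at about the same time as the last one.
- The Week 40 SGRQ example turns on one day. With EOT on days 278 to 280, 3 of the 7 permitted days, EOT falls in the Week 36 window, rule 1 moves it to Week 52, and the case becomes a collision. Only EOT Weeks 24 and 42 are affected for SGRQ and IgE at every permitted day.
- Only EOT at or before about Week 44 matters, so only later enrollees contribute.
- The outputs are within-group secondary summaries with no between-group test.
- SAP 7.2.2 summarises each collection point, and EOT and EOS are collection points, so separate summaries may already be intended.

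These points limit the scope and should be kept in view, but they do not remove the error. Neither reading is free of off-drug values in late cells, and the collisions are themselves a gap in the rules. The limitation to the treatment period in SAP 14.1 does not rescue section 11.4: the two sections conflict and nothing says which governs. A treatment-policy argument does not help either. That strategy is stated only for the primary endpoint, and a planned washout after completed treatment is not treatment discontinuation.

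**Conclusion.** The concern holds. Followed as written, section 11.4 can report measurements taken 14 weeks after the last dose as treatment-period results at Weeks 36, 44 and 52. At nominal days this occurs uncontested in 8, 7 and 4 of 14 shortened EOT weeks (FeNO; ACQ-5; SGRQ and both IgE), or in 7, 5 and 2 if the Week 52 code counts as observed.

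These are counts of possible schedules under the stated assumptions. The number of patients affected and the direction of bias cannot be determined from the documents. Week 44 is affected only for FeNO and ACQ-5. Drug concentration is affected only at the margin (EOT about Weeks 24 to 28, or a missing EOT sample), and its endpoint runs to end of study in any case. The primary FEV1 analysis is not affected for patients with an observed Week 24 value: after EOT at Week 24 or later, nominal EOS is day 253 or later, outside the Week 24 spirometry window of 121–197. This should be corrected, but it does not threaten the primary test.

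**What to change.** Amend SAP 11.4 as follows:

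1. Remove EOS from the mapping into the Week 36, 44 and 52 treatment-period cells, and report it only as a separate follow-up time point.
2. For Weeks 36 to 52, use an EOT or early termination value only for the visit whose window contains its actual study day, without moving it forward under rule 1. Leave the mapping up to Week 24, including primary FEV1, unchanged.
3. State that the Week 52, Visit 28 code is a database label and not an observed Week 52 value for patients whose treatment ended before Week 52.
4. State explicitly that EOT is summarised as its own time point.
5. Keep EOS samples out of the Week 52 drug-concentration cell. No matching change is needed for anti-drug antibody status, which SAP 10.6.2.1 does not derive from a Week 52 cell.

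The cost is SAP wording and programming, with no change to data collection. The statistical price is fewer patients in the Week 36 to 52 cells.

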#### 4.1.2. Secondary Endpoints

The secondary endpoints are:

- Annualized rate of severe respiratory exacerbations, defined as new onset of symptoms or clinical worsening of respiratory symptoms requiring systemic corticosteroid treatment for ≥3 consecutive days; for patients who are on maintenance systemic corticosteroids, at least double the dose of maintenance systemic corticosteroids for ≥3 consecutive days (with or without antibiotic therapy if indicated) over the 24- to 52-week treatment period
- 2. Annualized rate of ABPA-related exacerbations, defined as severe respiratory exacerbations (as defined above) that are associated with a doubling of serum total IgE from the prior pre-exacerbation value, over the 24- to 52-week treatment period
- 3. Annualized rate of severe respiratory exacerbations requiring either hospitalization or observation for >24 hours in an ED/urgent care facility during the 24- to 52-week treatment period
- 4. Change from baseline in ACQ-5 over the 24- to 52-week treatment period
- 5. Change from baseline in SGRQ total score over the 24- to 52-week treatment period
- 6. Percentage of participants achieving a reduction in the SGRQ score of 4 points or greater from baseline to weeks 12, 24, 36, and 52
- 7. Percent change from baseline in total IgE in serum over the 24- to 52-week treatment period
- 8. Percent change from baseline in *A fumigatus*-specific IgE in serum over the 24- to 52week treatment period
- 9. Percent and absolute change from baseline in FeNO over the 24- to 52-week treatment period
- 10. Incidence of treatment-emergent adverse events (TEAEs) from baseline through the end of treatment (week 24 to 52)
- 11. Immunogenicity of dupilumab, as determined by the incidence, titer, and clinical impact of treatment-emergent ADA to dupilumab over time
- 12. Concentrations of functional dupilumab in serum by treatment regimen at each assessment time point from baseline to the end of study

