# 6. STUDY DESIGN

### 6.1. Study Description and Duration

This phase 2, global, multicenter, randomized, double-blind, placebo-controlled study of dupilumab is designed to evaluate the efficacy and safety of dupilumab in patients with ABPA. Approximately 60 patients will be enrolled in the study. The study consists of 3 study periods:

- Screening period (4 weeks)
- Randomized treatment period (24- to 52 weeks)
- Post-treatment follow-up period (12 weeks)

This study employs a variable treatment duration from 24- to 52 weeks. Patients enrolled in the trial will remain in the treatment period for up to a maximum of 52 weeks or until the last patient completes a minimum treatment period of 24 weeks. Of note, the accrual and drop-out rates will be closely monitored. The maximum treatment duration of 52 weeks will not be changed. For further explanation regarding the duration of the randomized treatment period, refer to Section 9.1.1.

Patients who meet the eligibility criteria will be randomized (1:1) to 1 of the following treatment groups:

- Dupilumab 300 mg, after a loading dose of 600 mg on day 1, administered SC Q2W
- Matching placebo, administered SC Q2W

Randomization will be stratified by region (pooled country), chronic systemic corticosteroid use (yes/no) at screening, and by oral antifungal use (yes/no) at screening.

Rescue courses of systemic steroids for exacerbations, as determined by the investigators, will be permitted during the study. Patients will be required to continue all background asthma controller medications (ICS) with or without long-acting beta agonist (LABA), leukotriene receptor antagonist (LTRA), or long-acting muscarinic receptor antagonist (LAMA) without any changes in the dose or regimen during the study period. However, if 2 or more exacerbations occur during the treatment period, changes to background therapy (eg, changes to background asthma controller medication or initiation of antifungal therapy) may be made at the investigator's discretion.

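### SAP 11.4 can label a truncated patient's End of Treatment value as a week up to 14 weeks later, or assign it to no week, in the secondary-endpoint tables

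*SAP*

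**What the plan says.** **Treatment length.** Protocol 6.1: "Patients enrolled in the trial will remain in the treatment period for up to a maximum of 52 weeks or until the last patient completes" 24 weeks. When that point is reached, the footnotes to the protocol's schedule of events say that patients still on treatment "should return to the clinic 2 weeks from their last dose/treatment administration to complete their EOT visit". The schedule footnotes in SAP 14.2 add: "All patients must have their EOS visit 12 weeks after their EOT visit".

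**Endpoints.** Several secondary endpoints run over this variable period, for example "Change from baseline in SGRQ total score over the 24- to 52-week treatment period" (Protocol 4.1.2). The SGRQ responder endpoint is tied to Weeks 12, 24, 36 and 52.

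**Visit assignment (SAP 11.4).** EOT is coded as Week 52/Visit 28 "for all patients, regardless of the variable 24-52-week treatment period". EOT, EOS and early termination visits together are called ETTS visits and are reassigned by study day. Under rule 1, when the scheduled visit in that window already has a value, "the ETTS visit will be mapped to the next scheduled visit, provided there is no observed value of the parameter" at that next visit. A further sentence limits eligibility: "Only ETTS and unscheduled visits that occur within the analysis visit windows defined in" Table 3 may be assigned to a scheduled visit. The note under Table 3 restricts each parameter to the windows of visits at which it is analysed. Table 3 has no EOT row.

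**The concern.** For a patient whose treatment is cut short, EOT is the last planned treatment-period measurement, usually 2 weeks after the last dose. The assignment rules were built around fixed weeks. They can show that value as a week the patient never reached on treatment, or leave it outside every nominal week. The Week 36, 44 and 52 rows would then mix true treatment durations without saying so. Patients whose EOT falls in a gap would be absent from those rows.

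EOS is also an ETTS visit, 12 weeks after EOT and so about 14 weeks after the last dose for a patient dosed to the end. The same rules can place it in a treatment-period row. With about 30 patients per group, a few such values can shift a row's estimate.

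**Working it through.** **Inputs.** Windows from SAP Table 3; collection visits from SAP 7.1.3, 7.1.4 and 7.1.11; EOT and EOS timing from the schedule footnotes.

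**Reproducing the plan's figures.** Study day = 7 × week + 1 gives 169, 253, 309 and 365 for Weeks 24, 36, 44 and 52, matching Table 3. It also matches the other nine target days.

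**Windows from Week 24 on**

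| Parameter | Wk 24 | Wk 36 | Wk 44 | Wk 52 | Uncovered days |
|---|---|---|---|---|---|
| SGRQ, A fumigatus IgE | 141–197 | 225–280 | none | 338–393 | 198–224, 281–337 |
| ACQ-5 | 155–183 | 239–267 | 295–323 | 351–379 | 184–238, 268–294, 324–350 |
| FeNO | 121–197 | 198–295 | 296–337 | 338–393 | none |

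Total IgE has windows 141–197, 225–280, 281–337 and 338–393. It is not collected at Week 44, so on the Table 3 note its 281–337 window does not apply and its gaps equal those of SGRQ.

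**Check.** Place EOT at each even week from 26 to 50 (13 points; Week 52 is the untruncated case). Assume earlier scheduled visits were attended, and that an ETTS visit alone in an empty window fills it.

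| Parameter | Pushed to a later week by rule 1 | In no window | Fills its own window |
|---|---|---|---|
| SGRQ, A fumigatus IgE, total IgE | 3: 26→36 (+10), 28→36 (+8), 38→52 (+14) | 6: 30, 40, 42, 44, 46, 48 | 4: 32, 34, 36, 50 |
| ACQ-5 | 3: 26→36 (+10), 38→44 (+6), 46→52 (+6) | 5: 28, 30, 32, 40, 48 | 5: 34, 36, 42, 44, 50 |
| FeNO | 7: 26→36 (+10), 28→36 (+8), 38→44 (+6), 40→44 (+4), 42→44 (+2), 46→52 (+6), 48→52 (+4) | 0 | 6: 30, 32, 34, 36, 44, 50 |

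The 14-week case is EOT at Week 38: day 7 × 38 + 1 = 267 lies in the SGRQ Week 36 window. That window is already filled, and the next scheduled SGRQ visit is Week 52, day 365: (365 − 267)/7 = 14.

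**By day rather than week.** Of the 183 days from 183 to 365, SGRQ leaves 27 + 57 = 84 uncovered and ACQ-5 leaves 55 + 27 + 27 = 109.

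**Sensitivity.**
- If the Week 44 window were applied to total IgE, only Week 30 would be unassigned and the largest shift would be 10 weeks.
- Several points sit on a window edge. With the ±3-day visit window, an ACQ-5 EOT one day after day 183, 267 or 323 changes from pushed to unassigned.

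**EOS at EOT + 12 weeks.**
- EOT at Week 26: EOS is day 267, inside the Week 36 window for all five measures.
- EOT at Week 38: EOS is day 351, inside the Week 52 window for all five.
- EOT at Weeks 40, 42 and 44, for SGRQ and the IgEs: EOT is unassigned, while EOS on days 365, 379 and 393 falls in the Week 52 window. The off-drug value enters unopposed.

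In the first two cases EOS competes with a pushed EOT value, except for ACQ-5 and FeNO at Week 38, where EOT goes to Week 44. Rule 2a ranks EOT above EOS only when both lie in the same window.

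**The case against.** **An EOT summary may already be intended.** SAP 7.1.3, 7.1.4 and 7.1.11 list EOT as a collection point. SAP 7.2.2 and 14.1 promise estimates at each point of collection, the schedule has an EOT column, and parts of the text are redacted. A reader might infer that unassigned values are thrown away or that no EOT summary exists; the documents do not say either. This part of the objection stands. It does not settle the matter, because no text says how an EOT row is built once EOT is coded as Week 52 and reassigned by day. If the coded label were used, a Week 26 EOT would appear as Week 52. The SGRQ responder endpoint has no such way out, since its weeks are fixed.

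**The stakes are limited.** The primary MMRM stops at Week 24. The affected measures are within-group summaries, not compared with placebo and without multiplicity control. The three exacerbation rates use each patient's actual EOT date, and the Week 24 row remains a common time point. All of this stands and limits the severity.

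**The counts are not patients.** Six of 13 is a share of possible EOT weeks. The documents give no randomisation dates, so the number truncated could be small. This stands.

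**Who is affected.** A reader might infer that truncated patients entered under Amendment 2's wider criteria. They are the later enrolled, but no dates support the further step.

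**EOT is not always on drug.** For patients off study drug who stay in the study, EOT is 2 weeks from their last visit. Patients who leave the study early have an early termination visit and no EOT (SAP 5.2). This stands, and any EOT row must allow for it.

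**Conclusion.** The concern holds as a defect in the assignment rules for secondary endpoints, and it should be corrected. Followed as written, SAP 11.4 can relabel a truncated patient's EOT value by up to 14 weeks for SGRQ and both IgEs, and by up to 10 weeks for ACQ-5 and FeNO. It leaves 6 of 13 possible EOT weeks without a nominal week for SGRQ and the IgEs, 5 of 13 for ACQ-5 and none for FeNO. It can also admit an off-drug EOS value to Week 36 or 52.

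The effect is definite for the SGRQ responder endpoint at Weeks 36 and 52. For the other measures the SAP implies an EOT summary but gives no rule for it.

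The figures assume nominal visit days, attended scheduled visits and, for total IgE, that the Week 44 window is inapplicable. They say nothing about how many patients are affected. A reader might extend the point to the primary result; the documents do not support that when the Week 24 FEV1 value is observed.

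**What to change.** **SAP 11.4**
- Remove rule 1's push to the next scheduled visit for both EOT and EOS.
- Let EOT fill a nominal week only if its actual day lies in that week's own window and the scheduled value is missing.
- Do not let EOS fill any treatment-period row for efficacy, patient-reported or biomarker endpoints.

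Both visits must be covered. If only EOT were taken out of rule 1, EOS would fill Week 36 unopposed when EOT is at Week 26, and Week 52 for SGRQ and the IgEs when EOT is at Week 38.

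**SAP 7.2.2 and 14.1**
- Add an End of treatment row for ACQ-5, SGRQ change, SGRQ responders, both IgEs and FeNO, using the actual EOT value.
- Summarise treatment duration and time since last dose beside it, since EOT may follow the last dose by more than 2 weeks in patients already off study drug.
- Count patients who withdraw without an EOT visit as missing in that row.

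**Cost.** SAP wording and one row per table; no new data. The Week 36, 44 and 52 rows shrink: of the 13 EOT points, those filling a nominal week would be 4 for SGRQ and the IgEs, 5 for ACQ-5 and 6 for FeNO. The new row pools durations of 24 to 52 weeks, which is why duration must be shown with it. Ordinary within-window differences remain, such as a Week 30 FeNO value shown at Week 36.
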